### CREATION OF A NEW INDICATOR VARIABLE

Patients fulfilling inclusion and non-inclusion criteria will be considered as **ELIGIBLE (ELI= 1)**.

#### New binary variable ELI

Label: « Eligibility based on CRF»

**ELI= 1** if the patient is eligible

**ELI= 0** if the patient is not eligible

## **3 STATISTICAL METHODS**

### **3.1 STATISTICAL ANALYSIS**

#### **3.1.1 DOSE ESCALATION AND EXPANSION COHORT PART**

- Patient characteristics at baseline will be provided
  - Compliance with eligibility criteria,
  - Epidemiological characteristics,
  - Clinical and laboratory characteristics,
  - Treatment characteristics.
- Toxicities will be recorded in terms of event type, severity, dates of beginning and end, reversibility and evolution. Data will be gathered in tables summarizing toxicities and side effects for each dose level and cycle.
- Efficacy analysis: efficacy endpoints will be reported in terms of counts and proportions for each dose levels.
- All analyses will be descriptive; no p-values will be calculated.
- For continuous variables, summary statistics will include number of patients, median, minimum, and maximum, and additional percentiles if appropriate.
- Categorical endpoints will be summarized using number of patients, frequency, percentages.
- For survival endpoints, median survival time will be reported.
- Missing data will not be imputed.

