
DOSE ESCALATION PART

Regimen description:

Concomitant treatment by continuous Olaparib and radiotherapy.

- Olaparib will be given orally, continuously, twice a day, as appropriate for assigned dose level, from Day1 to the end of radiotherapy. Olaparib will be started one week before the start of radiotherapy and will be continued until the last day of radiotherapy. Beyond this period, Olaparib could be continued at the investigator's discretion and after sponsor authorization, until progression.
- Radiotherapy consists of fractionated focal irradiation at a dose of 1.8 Grays (Gy) per fraction given once daily five days per week (Monday through Friday), for a total dose of 59.4 Gy (ie. 33 fractions). Radiotherapy starts at D8.

Dose levels

- Dose escalation study assessing 4 doses level of Olaparib in association with

Level	-1	1	2	3	4
Olaparib	25 mg (daily)	25 mg (b.i.d)	50 mg (b.i.d)	100 mg (b.i.d)	150 mg (b.i.d)

concomitant radiotherapy.

- The starting dose of Olaparib is 25 mg b.i.d.
- The maximum dose of Olaparib administered (150 mg x 2) will not be exceeded.
- No skipping of the dose will be allowed.
- For a given patient, dose will never be escalated.
- **As long as no DLT is observed** patients will be allocated to 4 dose levels following a 3+3 design with the following characteristics:
 - Inclusions of cohorts of 3 patients,
 - At dose levels 1 and 2, before accrual to next higher dose level, at least 2 patients with 6-week follow-up will be required,
 - At dose level 3, before accrual to dose level 4, at least 2 patients with 8-week follow-up will be required
- **As soon as the first DLT is observed**, patients will be allocated following a TITE-CRM design [Normolle et al. Statistics in Medicine 2003]. When a patient is eligible for enrollment, the probability of DLT is estimated for each dose level, based on the trial experience up to that time and the prior expectations for toxicity.
 - Each new patient is assigned to the currently estimated target dose, defined as the dose having an estimated probability of toxicity closest to but not greater than the target rate (33%), subject to the following restrictions :
 - A minimum of 2 patients will be entered on each dose level,
 - At dose levels 1 and 2, before accrual to next higher dose level, at least 2 patients with 6-week follow-up will be required,
 - At dose level 3, before accrual to next higher dose level, at least 2 patients with 8-week follow-up will be required,

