
	
13. Patients with myelodysplastic syndrome/acute myeloid leukaemia,
 
14. Major surgery within 14 days of starting study treatment,
 
15. Participation to a study involving a medical or therapeutic intervention in the last 30 days,
 
16. Patient unable to follow and comply with the study procedures because of any geographical, familial, social or psychological reasons,
 
17. Previous enrollment in the present study,
 
18. Patients with a known hypersensitivity to olaparib or any of the excipients of the product,
 
19. Patients who not have recovered from any effects of any major surgery,
 
20. Individuals deprived of liberty or placed under legal guardianship.
 
21. Patients who have tumor in contact with, invading or encasing for more than 50% any major blood vessels and/or patients requiring vascular reconstruction.
																												
Route of administration	
Olaparib will be administered per os bi-daily, as appropriate assigned dose level, during 7.5 weeks (D1 to D52). Olaparib should be started one week before the start of radiotherapy and will be continued until the last day of radiotherapy. Beyond this period, Olaparib could be continued at the investigator’s discretion and after sponsor authorization, until progression.
 
Radiotherapy consists of fractionated focal irradiation: During Dose escalation: At a dose of 1.8 Grays (Gy) per fraction given once daily five days per week (Monday through Friday) over a period of 6.5 weeks, for a total dose of 59.4 Gy. Radiotherapy starts at D8.
 
During expansion cohort: Resecable tumors: At a dose of 2 Grays (Gy) per fraction given once daily five days per week (Monday through Friday) over a period of 5 weeks, for a total dose up to 50 Gy. Radiotherapy starts at D8. Unresecable tumors: At a dose of 1.8 Grays (Gy) per fraction given once daily five days per week (Monday through Friday) over a period of 6.5 weeks, for a total dose of 59.4 Gy. Radiotherapy starts at D8.
																												

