3.4.1. Treatment scheme and DLT observation period

- Olaparib will be given orally, continuously, twice a day, as appropriate for assigned dose level, from D1 to the end of radiotherapy. Olaparib will be started one week before the start of radiotherapy and will be continued until the last day of radiotherapy. Beyond this period, Olaparib could be continued until progression, at the investigator's discretion and sponsor approval.
- Radiotherapy consists of fractionated focal irradiation at a dose of 1.8 Grays (Gy) per fraction given once daily five days per week (Monday through Friday), for a total dose of 59.4 Gy (i.e 33 fractions). Radiotherapy starts at D8.
- The DLT observation period is defined as the first day of Olaparib intake and up to 6 weeks after the end of radiotherapy (13.5 weeks).

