9. AEs	As per NCI-CTCAE, version 4.	Throughout the treatment period

*For all laboratory tests a window of 72 hours will be allowed.

ALT, alanine aminotransferase; ANC, absolute neutrophil count; AP, alkaline phosphatase; aPTT, activated partial thromboplastin time;

	ASSESSMENT	TIME
AST, aspartate aminotransferase; ECG, electrocardiogram; ECOG PS, Eastern Cooperative Oncology Group Performance Status; INR, International Normalized Ratio; LDH, lactate dehydrogenase; MCH, mean cell haemoglobin; MCHC, mean cell haemoglobin concentration; MCV, mean cell volume; MRI, magnetic resonance imaging; RBC, red blood cell; RECIST v1.1, Response Evaluation Criteria In Solid Tumors; TP, prothrombin Rate; WBC, white blood cells.		

5.6.EVALUATION AT END OF TREATMENT

The end-of-treatment visit will be scheduled:

- 30 days (4 weeks) after the last Olaparib administration (a window of ± 1 week is allowed) and/or
- 6 weeks after the last dose of radiotherapy.

Regardless of the reason for discontinuation, the complete workup has to be done at the end-of-treatment visit. This will include the following assessments:

- Assessment of signs and symptoms.
- Complete physical examination.
- ECOG performance status.
- Vital signs [heart rate, blood pressure, and temperature].
- Hematology.
- Biochemistry.
- Calculated CrCl.
- Electrocardiogram (QTc measurement: twelve-lead ECGs will be obtained after the patient has been rested in a supine position for at least 5 minutes. ECGs will be recorded at 25 mm/sec.)
- Clinical and radiological tumor assessment (MRI and CT Scan if metastatic disease at inclusion) (except for patients with confirmed PD at discontinuation or who had started a new treatment).
- Intercurrent events and concomitant disease and treatments.
- Safety assessment (AEs).

Adverse events must be reported for 30 days after the last dose of Olaparib and/or 6 weeks after the last dose of radiotherapy administration or until the start of a new antitumor therapy, whichever occurs first. All SAEs occurring within 30 days after the last dose of Olaparib and/or 6 weeks after the last dose of radiotherapy or until the start of a new antitumor therapy, whichever occurs first, will be reported. Beyond this period of time, only those SAEs suspected to be treatment-related (Olaparib/radiotherapy) or research-related (diagnostic procedures, examinations carried out during the research...) will be reported (see Section 11).

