## 3.2 ENDPOINT ANALYSIS

### 3.2.1 PRIMARY ENDPOINT

#### 3.2.1.1 DOSE ESCALATION PART

- Toxicity graded using the common toxicity criteria from the NCI v4.03.
- Incidence rate of DLT at each dose level during treatment period up to six weeks after end of radiotherapy.

Criteria	eFORM variable	Control
Toxicity	EXA_RAD TOXI_RA EXA_ON TOXI_ON AEV4 AEVENT, AEECI (clinically interesting), DT_EIC, SOC, AESAE DT_SAE , DT_AE, DTENDAE (date of the end or death), INIT_INT, MAX_INT	
Check if the following variables are completed :
 
TOXI_RA TOXI_ON AEVENT AEECI DT_EIC SOC AESAE DT_SAE , DT_AE DTENDAE INIT_INT, MAX_INT
 
Data will be gathered in tables summarizing toxicities and side effects for each dose level and cycle.

Incidence rate of DLT	EXA_RAD DLT_RA EXA_ON DLT_ON DS_TOX DS_C10L (dose Olaparib) DT_TOX (Date tox)	
Check if the following variables are completed :
 
DLT_RA DLT_ON DS_C10L DT_TOX

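### Toxicity percentages by dose level have no common observation window, so they reflect time on olaparib as well as dose

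*SAP*

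**What the plan says.** **Length of AE reporting.** Protocol 5.6 states: "Adverse events must be reported for 30 days after the last dose of Olaparib and/or 6 weeks after the last dose of radiotherapy administration". Reporting closes sooner if another antitumor treatment begins first. The same *and/or* appears in Protocol 5.2 (several times), 8.3 and 11.3. Olaparib is planned from D1 to D52 in the escalation part, but Protocol 3.4.1 adds: "Beyond this period, Olaparib could be continued until progression". The synopsis likewise leaves continuation to the investigator's "discretion and after sponsor authorization, until progression".

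**Endpoints.** Protocol 9.1 and SAP 3.2.1.1 list two primary endpoints for the escalation part. One is time-bounded: "Incidence rate of DLT at each dose level during treatment period up to six weeks after end of radiotherapy". The other is graded toxicity, with no time limit.

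**Tabulation.** SAP 3.1.1 says: "Data will be gathered in tables summarizing toxicities and side effects for each dose level and cycle", and SAP 3.2.1.1 repeats this for the primary toxicity endpoint. The summary measure is: "Categorical endpoints will be summarized using number of patients, frequency, percentages". The AE tables in SAP 4.2.10 count patients or events by term and grade. Their titles name no dose level, cycle or period, whereas the DLT tables in SAP 4.2.9 are by dose level.

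**Use.** Protocol 3.3 bases the RP2D on the MTD plus further safety data, acute and late, and pools escalation and expansion patients.

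**The concern.** A percentage of patients with an AE depends on how long each patient was watched. Here that time follows olaparib, and time on olaparib depends on progression, tolerance and the investigator's choice. If continuation differs between dose levels, the toxicity columns will differ even where the underlying risk does not, and a real difference can be hidden. The protocol minimum is 2 patients per level, where one patient is worth 50 percentage points (1/2).

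Splitting by cycle would give some control for time, but the term has no length, so the table cannot be programmed as written.

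A second problem lies in the *and/or*. If the 30-day limb is applied alone, routine AE reporting could close before the DLT window does. What is at stake is the general toxicity profile that the steering committee sets beside the MTD when it chooses the RP2D.

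**Working it through.** **1. The plan's own window.** One week of olaparib lead-in + 6.5 weeks of radiotherapy + 6 weeks = 13.5 weeks, as Protocol 3.4.1 states. By days: 59.4 Gy / 1.8 Gy = 33 fractions. At five a week from D8, 30 fractions end on D47 and the last three fall on D50 to D52. Then 52 + 42 = D94, and 94/7 = 13.4 weeks, which agrees.

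**2. Where AE reporting ends.** Protocol 7.2.4 gives resectable expansion patients 25 fractions, so their last is on D40.

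| Patient | 30-day limb | 6-week limb |
|---|---|---|
| 33 fractions, olaparib stops D52 | 52 + 30 = D82 | 52 + 42 = D94 |
| 25 fractions, olaparib stops D40 | 40 + 30 = D70 | 40 + 42 = D82 |
| Olaparib to week 24 | 24 + 30/7 = 28.3 weeks | already past |
| Olaparib to week 52 | 52 + 30/7 = 56.3 weeks | already past |

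Against 13.4 weeks, continuers are observed 28.3/13.4 = 2.1 and 56.3/13.4 = 4.2 times as long. For a 33-fraction patient who stops at D52, the 30-day limb ends 94 − 82 = 12 days before the DLT window closes.

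**3. Effect on a crude percentage (illustration).** The documents give neither AE hazards nor the share who continue, so both are assumed. With a constant hazard, h = −ln(1 − p)/13.4, where p is the proportion with the AE by week 13.4. A continuer observed for T weeks has probability 1 − exp(−hT). If a share f continues, the level reads (1 − f)p + f[1 − exp(−hT)].

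| p by week 13.4 | f = 25%, to wk 24 / wk 52 | f = 50%, to wk 24 / wk 52 | f = 100%, to wk 24 / wk 52 |
|---|---|---|---|
| 20% | 24.4% / 30.2% | 28.8% / 40.4% | 37.5% / 60.8% |
| 30% | 35.7% / 41.9% | 41.4% / 53.8% | 52.8% / 77.6% |
| 40% | 46.5% / 52.1% | 53.0% / 64.1% | 65.9% / 88.2% |

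For p = 30% and f = 50% to week 24: h = 0.357/13.4 = 0.0266 per week; 1 − exp(−0.0266 × 28.3) = 0.528; 0.5 × 0.30 + 0.5 × 0.528 = 0.414.

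**4. Masking (extreme illustration).** Give a lower level hazard h (p = 30%) with everyone continuing to week 24: it reads 53%. Give a higher level hazard 2h with everyone stopping at D52: it reads 1 − 0.70² = 51%. A doubled hazard disappears.

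**5. With a common window.** At p = 30%, two levels with equal hazard both read 30% by week 13.4, or 2.66 first events per 100 patient-weeks, whatever share continues.

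**6. The undefined cycle.** Dosing is continuous (Protocol synopsis and 7.1.3) and dispensing is monthly (7.1.3). Protocol 17.1.1 labels PK days as days of cycle 1, and Appendix 3 requires one cycle for response evaluability. None of these gives a cycle length.

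**The case against.** The strongest reply is that the dose decision is largely protected. DLT incidence, which sets the MTD, has a fixed window that continuation cannot stretch. The RP2D is a steering-committee judgement put to the IDMC, not a formula on AE percentages. All analyses are descriptive, olaparib weeks and cumulative dose are tabulated by dose level (SAP 4.2.5), and AE listings with dates are foreseen if required (SAP 4.1.5). All of this stands and limits the point to the general toxicity tables. It does not supply the missing window, because exposure is never linked to the AE tables.

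The constant hazard is also open to attack. Radiotherapy ends at D52; Protocol 7.2.5 and 11.9 describe much of its toxicity as acute, and 7.1.6.8 says nausea and vomiting generally start in the first month. For such events the illustration overstates the drift. A bias between levels also needs continuation to differ between them, which nothing in the documents shows.

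On the *and/or*, every patient treated to plan has radiotherapy, so the 6-week limb can be read as applying to all. The schedule records AEs throughout the study, and toxicity examinations run to D92 (7.2.5). A reader might infer that DLT data will be lost after D82. The documents do not show that; they show wording that permits it.

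Finally, Protocol 10.3 uses the cycle wording only for the expansion cohort, where all patients are assigned one olaparib dose. The between-dose problem therefore rests on SAP 3.1.1 and 3.2.1.1.

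**Conclusion.** The point holds for the all-AE tables: as planned, toxicity percentages by dose level combine patients observed to about D94 with patients who may be observed for a year or more. The direction and size of any distortion are unknown. The 41% and 54% readings of a 30% risk rest on an assumed constant hazard and on half of a level continuing.

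Two stronger inferences are tempting and unsupported. One is that the rates would follow time on drug instead of dose; they would follow both. The other is that the MTD is compromised; its DLT rate is measured on a fixed window. Pooling for the RP2D adds a further mismatch, because 25-fraction patients have a shorter window (about D82) than 33-fraction patients (about D94).

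This is a cheap improvement worth making, not a flaw in the dose-finding design.

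**What to change.** - **SAP 3.1.1, 3.2.1.1 and 4.2.10.** Tabulate escalation toxicity by dose level on the existing DLT window (first olaparib dose to 6 weeks after radiotherapy, 13.5 weeks), and put the dose level and window in the table titles.
- **Later AEs.** Report them in a separate table by dose level, with patient-months of observation.
- **Cycle.** Replace it with stated calendar periods.
- **Pooled data for the RP2D.** Show 25-fraction and 33-fraction patients separately, or use one fixed-day window for all.
- **Protocol 5.2, 5.6, 8.3 and 11.3.** Reconcile the *and/or* wording in all four sections so that AE reporting covers at least the full DLT window. State how this combines with the cut-off at a new antitumor therapy.

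No new data are needed, since SAP 3.2.1.1 already lists AE and SAE dates. The cost is one extra table, which will be sparse, and some rewording in both documents.

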#### **3.1.2 PHARMOCOKINETICS AND PHARMACODYNAMICS**

- Pharmacokinetics
  - PK analyses will be based on all subjects who receive at least one dose of Olaparib, if appropriate. Deviations from this will be documented.
  - PK parameters (AUC, Cmax, t1/2) of Olaparib will be calculated using noncompartmental methods, and the systemic clearance (CL) will be derived from the plasma concentrations via standard methods.
  - All pharmacokinetic parameters will be presented descriptively including arithmetic means, standard deviations, geometric means, and coefficients of variation, medians and ranges.
- Pharmacodynamics (translational research). Given the small number of subjects, analyses will be descriptive. The distribution of the biomarkers will be reported for subgroups of patients defined by their response to treatment.

## 3.2 ENDPOINT ANALYSIS

### 3.2.1 PRIMARY ENDPOINT

#### 3.2.1.1 DOSE ESCALATION PART

- Toxicity graded using the common toxicity criteria from the NCI v4.03.
- Incidence rate of DLT at each dose level during treatment period up to six weeks after end of radiotherapy.

Criteria	eFORM variable	Control
Toxicity	EXA_RAD TOXI_RA EXA_ON TOXI_ON AEV4 AEVENT, AEECI (clinically interesting), DT_EIC, SOC, AESAE DT_SAE , DT_AE, DTENDAE (date of the end or death), INIT_INT, MAX_INT	
Check if the following variables are completed :
 
TOXI_RA TOXI_ON AEVENT AEECI DT_EIC SOC AESAE DT_SAE , DT_AE DTENDAE INIT_INT, MAX_INT
 
Data will be gathered in tables summarizing toxicities and side effects for each dose level and cycle.

Incidence rate of DLT	EXA_RAD DLT_RA EXA_ON DLT_ON DS_TOX DS_C10L (dose Olaparib) DT_TOX (Date tox)	
Check if the following variables are completed :
 
DLT_RA DLT_ON DS_C10L DT_TOX

### 3.2.1.2 EXPANSION COHORT

6-month non progression, defined as complete (CR) or partial response (PR) at 6 months confirmed  $\geq 4$  weeks after initial documentation, or stable disease more than 24 weeks (RECIST v1.1, as determined by investigator review of tumor assessments).

For the expansion cohort, radiological data will be centrally reviewed. The primary analysis will be based on reviewed data.

Criteria	eFORM variable	Control
6-month non progression	TUM_CYC (TUMOR ASSESSMENT) DT_MEAC (date of measurement) ME1L_ME5L (measures of lesions) SUM_TL (largest diameters) EVA1LNM_EVA5LNM (non-measurable lesions eval) RES_TL, RES_NTL (target and non-target lesions) OV_RESP (overall response) CR=1, PR=2, SD=3 TRT_OLA DT_S10 (D1 Olaparib)	DT_S10 filled in ME1L_ME5L (filled in if needed) SUM_TL filled in EVA1LNM_EVA5LNM (filled in if needed) RES_TL, RES_NTL (filled in) and check recist1.1 criteria  check for each patient (( DT_MEAC-DT_S10 $\geq 6$ ) and OV_RESP =(1 or 2 or 3)) Count number of non-progression case

### 3.2.2 SECONDARY ENDPOINT

#### 3.2.2.1 DOSE ESCALATION PART

Antitumor activity observed with Olaparib given in association with radiotherapy in terms of

- 6-month non progression, defined as complete (CR) or partial response (PR) at 6 months confirmed  $\geq 4$  weeks after initial documentation, or stable disease more than 24 weeks (RECIST v1.1, as determined by investigator review of tumor assessments)
- 6-month objective response, defined as CR or PR at 6 months confirmed  $\geq 4$  weeks after initial documentation, as determined by investigator review of tumor assessments using RECIST v1.1
- Best objective response under treatment is defined as complete (CR) and partial response (PR) recorded from the start of study treatment until the treatment with confirmation  $\geq 4$  weeks after initial documentation, as per RECIST 1.1. Objective response under treatment is determined once all the data for the patient is known.
- Best response under treatment is defined as the best response (CR, PR, SD) as per RECIST 1.1 recorded from the start of the study treatment until the end of treatment taking into account any requirement for confirmation as per RECIST v1.1 criteria. It is determined once all the data for the patient is known.
- 1-year Progression-free survival (PFS): PFS is defined as the time from study treatment initiation to the first occurrence of disease progression or death (of any cause), whichever occurs first.

- 1-year Overall Survival (OS): OS is defined as the time from study treatment initiation to death (of any cause).
- Functional assessment
  - Graded using the Musculoskeletal Tumour Society Rating Scale (Enneking, Modification of the system for functional evaluation in the surgical management of musculoskeletal tumours. In: Enneking WF, ed. Limb Salvage in Musculoskeletal Oncology. New York, NY: Churchill Livingstone, 1987:626A39.
  - MSTS will be completed by the radiotherapist at baseline and at the end of radiotherapy treatment.
  - The MSTS score is calculated from 6 functional criteria.
    - Three subjective criteria are common to the upper and lower limbs: pain, function, emotional acceptance of the surgical procedure (psychological acceptance).
    - The other three are objective criteria:
      - For the lower limb: support, walking and gait.
      - For the upper limb: the position relative to shoulder, dexterity, muscle strength
    - Each criterion is evaluated with a question (eg, pain is assessed by the consumption of analgesic drugs). The evaluation of each test contains six levels of achievement or scores, four defined scores (0, 1, 3, 5) and two intermediate (2, 4). The four scores are defined the score 5: absence of impact; the score 3: minor impact; the score 1: major repercussions; the score 0: disability.
  - Concerning the analysis of MSTS,
    - The total score will be described at each measurement time
    - A difference of 10 points or more will be used to define a clinically significant difference. There is particular focus on the difference between the observed scores before surgery and 1 year post surgery.
- PK measurements expressed as AUC, half-life and concentration peak for Olaparib.

Criteria	eFORM variable	Control
6-month non progression	TUM_CYC (TUMOR ASSESSMENT) DT_MEAC (date of measurement) ME1L_ME5L (measures of lesions) SUM_TL (largest diameters) EVA1LNM_EVA5LNM (non-measurable lesions eval) RES_TL, RES_NTL (target and non-target lesions) OV_RESP (overall response) CR=1, PR=2, SD=3 TRT_OLA DT_S10 (D1 Olaparib)	DT_S10 filled in ME1L_ME5L (filled in if needed) SUM_TL filled in EVA1LNM_EVA5LNM (filled in if needed) RES_TL, RES_NTL (filled in) and check recist1.1 criteria  check for each patient (( DT_MEAC-DT_S10 ≥ 6 ) and OV_RESP =(1 or 2 or 3))  Check confirmation ≥ 4 weeks  Count number of non-progression case

6-month objective response	TUM_CYC (TUMOR ASSESSMENT) DT_MEAC (date of measurement) ME1L_ME5L (measures of lesions) SUM_TL (largest diameters) EVA1LNM_EVA5LNM (non-measurable lesions eval) RES_TL, RES_NTL (target and non-target lesions) OV_RESP (overall response) CR=1, PR=2 TRT_OLA DT_S10 (D1 Olaparib)	DT_S10 filled in ME1L_ME5L (filled in if needed) SUM_TL filled in EVA1LNM_EVA5LNM (filled in if needed) RES_TL, RES_NTL (filled in) and check recist1.1 criteria  check for each patient (( DT_MEAC-DT_S10 ≥6 ) and OV_RESP =(1 or 2))  Check confirmation ≥ 4 weeks  Count number of objective case
Best objective response	TUM_CYC (TUMOR ASSESSMENT) DT_MEAC (date of measurement) ME1L_ME5L (measures of lesions) SUM_TL (largest diameters) EVA1LNM_EVA5LNM (non-measurable lesions eval) RES_TL, RES_NTL (target and non-target lesions) OV_RESP (overall response) CR=1, PR=2 TRT_OLA DT_S10 (D1 Olaparib)	DT_S10 filled in ME1L_ME5L (filled in if needed) SUM_TL filled in EVA1LNM_EVA5LNM (filled in if needed) RES_TL, RES_NTL (filled in) and check recist1.1 criteria  check the response for each patient across all time points OV_RESP =(1 or 2)  Check confirmation ≥ 4 weeks
Best response	TUM_CYC (TUMOR ASSESSMENT) DT_MEAC (date of measurement) ME1L_ME5L (measures of lesions) SUM_TL (largest diameters) EVA1LNM_EVA5LNM (non-measurable lesions eval) RES_TL, RES_NTL (target and non-target lesions) OV_RESP (overall response) TRT_OLA DT_S10 (D1 Olaparib)	DT_S10 filled in ME1L_ME5L (filled in if needed) SUM_TL filled in EVA1LNM_EVA5LNM (filled in if needed) RES_TL, RES_NTL (filled in) and check recist1.1 criteria  check the response for each patient across all time points OV_RESP =(1 or 2 or 3) Check confirmation ≥ 4 weeks  Data will be gathered in tables summarizing number of CR, PR, SD, PD
Progression-free survival (PFS)	END OF TREATMENT FORM DT_STA (Date of start of Olaparib) EOT_STA (Status) EOT_REA (Reason end) DT_PROG (Date of progression) END OF STUDY (END_STU)	Check if everything is filled in and If (DT_PROG is NA) then { If (PRO_LAS=0) then { PFS= DT_EOS-DT_STA ; If (EOS_REA = 'death') then IND_PFS=1 } }

	DT_EOS (date of end of study) FOLLOW UP FORM DT_FUP (date of visit) STA_FUP (Vital status) PRO_LAS, DT_FPRO (date of progression) DT_LNEW DT_DEAT END OF STUDY (END_STU) DT_EOS (date of end of study) EOS_REA (reason)	Else IND_PFS=0 } Else { PFS=DT_FPRO – DT_STA; IND_PFS=1} } Else { PFS= DT_PROG – DT_STA; IND_PFS=1}
Overall Survival (OS)	END OF TREATMENT DT_STA (Date of start of Olaparib) EOT_STA (Status) EOT_REA (Reason end) FOLLOW UP FORM DT_LNEW / DT_DEAT STA_FUP (Vital status) END OF STUDY (END_STU) DT_EOS (date of end of study) EOS_REA (reason) DT_DEATH (date of death)	If (STA_FUP NE 'dead') then do; if (EOS_REA='death') then { OS= DT_DEATH-DT_STA; IND_OS=1; } Else {OS= DT_EOS-DT_STA; IND_OS=0; } end; Else { OS= DT_DEAT-DT_STA; IND_OS=1; }
Functional assessment	EXA_RAD MSTS_RA (msts score)	Check if MSTS_RA is completed by the radiotherapist at baseline and at the end of radiotherapy treatment.

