#### **4.2.11 EFFICACY: Response, Progression and Survival**

- Table 14.1. Frequency distribution of objective response on population evaluable for efficacy
- Table 14.2. Frequency distribution of 6-month non-progression on population evaluable for efficacy

- Table 14.3. Frequency distribution of progression at one year on population evaluable for efficacy
- Table 14.4. Frequency distribution of deaths at one year on population evaluable for efficacy
- Table 14.5. Median follow-up time on population evaluable for efficacy– Life table
- Table 14.6. Median progression-free survival on population evaluable for efficacy – Life table
- Table 14.7. Median overall survival on population evaluable for efficacy – Life table

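### The SAP's PFS derivation does not implement its own definition for deaths, PFS and OS are both censored at the end-of-study date, and no 12-month Kaplan-Meier estimate is named for the 1-year endpoints

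*SAP*

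**What the plan says.** **Definitions (SAP 3.2.2.1).** "PFS is defined as the time from study treatment initiation to the first occurrence of disease progression or death (of any cause), whichever occurs first". For survival, "OS is defined as the time from study treatment initiation to death (of any cause"). Both endpoints are labelled 1-year. SAP 3.2.2.2 applies the same derivations to the expansion cohort.

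**PFS derivation (same section, Control column).** A progression date on the end-of-treatment form (DT_PROG) gives an event on that date. If it is absent, the next test is "If (PRO_LAS=0) then", on a follow-up-form field. When that test is met, "PFS= DT_EOS-DT_STA", with an event if the end-of-study reason is death and censoring otherwise. In every other case "PFS=DT_FPRO – DT_STA", with the event flag set to 1. The follow-up fields STA_FUP (vital status), DT_DEAT and DT_LNEW appear among the PFS inputs, but no branch uses them.

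**OS derivation.** A death on the follow-up form is dated by DT_DEAT. Failing that, an end-of-study reason of death is dated by DT_DEATH. Everyone else goes to "Else {OS= DT_EOS-DT_STA" and is censored. DT_LNEW is again listed and unused.

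**Reporting.** "For survival endpoints, median survival time will be reported" (SAP 3.1.1). The SAP synopsis plans Kaplan-Meier analysis with 95% intervals for medians, section 4.2.11 plans life tables (14.5 to 14.7), and section 4.3 plans Kaplan-Meier curves. The only 1-year outputs are "Table 14.3. Frequency distribution of progression at one year on population evaluable for efficacy" and its counterpart for deaths, Table 14.4.

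**The concern.** The PFS definition counts any death. The code recognises a death only through one gate (PRO_LAS equal to 0) and one form (end of study), and takes the date from study closure. The neighbouring OS code reads deaths from both forms and uses actual death dates. The SAP therefore does not treat the two forms as interchangeable, nor the closure date as the death date.

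Followed literally, the same patient can be dead for OS and event-free for PFS, or have a PFS time longer than the OS time, which the definitions rule out.

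Censoring at the end-of-study date credits patients with event-free or survival time for which there may be no scan and no contact. A 1-year frequency count does not account for patients lost before one year. With cohorts of about 14 to 24 assessable patients, one misclassified patient visibly moves the result.

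**Working it through.** The plan attaches no event count, power or precision to PFS or OS, so there is no stated figure to reproduce. The check is a trace of the printed logic plus three illustrations.

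**1. Trace.** Nesting is read from the If/Else sequence. Days run from DT_STA. The patients are constructed. The first two rows assume that PRO_LAS is missing when no follow-up form exists.

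| Patient | PFS (day, event) | OS (day, event) |
|---|---|---|
| Death day 60, no follow-up form, end-of-study reason death | missing, 1 | 60, 1 |
| Withdrawal day 60, no follow-up form | missing, 1 | 60, 0 |
| Death day 200 on follow-up form, PRO_LAS=0, end-of-study reason not death, closed day 365 | 365, 0 | 200, 1 |
| Same death, end-of-study reason death, closed day 230 | 230, 1 | 200, 1 |
| Alive, last scan day 168, last news day 260, lost, closed day 365 | 365, 0 | 365, 0 |
| Progression day 180 on follow-up form, alive, closed day 365 | 180, 1 | 365, 0 |

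The last row is handled correctly. In rows 3 and 4, PFS exceeds OS. In row 5, PFS credit runs 365 − 168 = 197 days past the last scan, and OS credit runs 365 − 260 = 105 days past last news.

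**2. Early deaths dropped from PFS.** Take n = 14 (the expansion cohort's assessable number, SAP synopsis), 6 other events within a year, no other censoring, and k early deaths without a follow-up form who belong to the evaluable population. A record with no time cannot enter the Kaplan-Meier estimate. Correct 1-year PFS is 1 − (6 + k)/14. As coded it is 1 − 6/(14 − k).

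- k = 1: 1 − 7/14 = 50.0%, against 1 − 6/13 = 53.8%
- k = 2: 1 − 8/14 = 42.9%, against 1 − 6/12 = 50.0%
- k = 3: 1 − 9/14 = 35.7%, against 1 − 6/11 = 45.5%

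**3. One patient lost early but counted event-free.** With m of 14 counted event-free, the crude figure is m/14. If that patient is instead censored before any event, the Kaplan-Meier figure is (m − 1)/13; later censoring can only raise it. The gap is therefore at most m/14 − (m − 1)/13 = (14 − m)/182. At m = 7 this is 7/182, about 3.8 points (50.0% against 46.2%).

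**4. Crude 1-year frequency under loss to follow-up.** The documents give no event or loss rates, so exponential times are assumed. Let S be the true 1-year event-free rate, L the 1-year loss probability in the absence of events, λ = −ln S and μ = −ln(1 − L). The expected crude event frequency over all patients is λ/(λ + μ) × [1 − e^−(λ+μ)]. For S = 50% and L = 10%: λ = 0.693, μ = 0.105, giving 0.868 × 0.550 = 47.7% against the true 50.0%, a shortfall of 2.3 points.

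| S | Shortfall at L = 10% | Shortfall at L = 30% |
|---|---|---|
| 30% | 2.9 points | 9.1 points |
| 50% | 2.3 points | 7.1 points |
| 70% | 1.4 points | 4.5 points |

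With no loss before one year the crude frequency is exact.

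**The case against.** Several parts of the case against are sound.

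- **The CRF is not visible.** The follow-up form holds vital status, death date and last news, so it may be completed even for a death on treatment. The PFS row also begins by asking that all fields be checked for completeness. The missing-time result is therefore conditional. It is not dismissed, because follow-up visits begin only after treatment discontinuation (Protocol 5.2 and 5.7) and the SAP gives no rule for a patient without one.
- **The forms will usually agree.** Follow-up runs until death, and the end-of-study listing (SAP 4.1.7) covers death and cause. A follow-up death wholly missed for PFS should be uncommon. Agreement does not cure the date, however: the code uses DT_EOS although the end-of-study form has its own DT_DEATH, which the OS code uses.
- **Layout.** The printed braces do not balance across a page break. This may come from text extraction and is not counted as an error.
- **Low stakes.** PFS and OS are secondary and descriptive, and the expansion decision rests on at least one non-progression.

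A reader might also infer more than the documents support:

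- *That OS loses deaths too.* It does not: it reads both forms and dates each death properly. Its only defect here is the censoring date.
- *That every flaw inflates PFS.* The same Else branch also removes early withdrawals. Dropping a censored patient leaves the Kaplan-Meier estimate unchanged or lowers it.
- *That the SAP offers only medians and crude counts.* Kaplan-Meier analysis, life tables and curves are planned. How Tables 14.3 and 14.4 treat lost patients is not stated.
- *That one lost patient adds a full 1/14, or 7 points.* That would need events in all 13 others.

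**Conclusion.** The PFS derivation contradicts the PFS definition and should be corrected. Three things follow from the text alone: deaths without progression are dated by study closure, the follow-up death fields are ignored, and event-free patients are censored at end of study rather than at the last tumour assessment. Where the forms disagree on death, or closure falls after death, PFS can exceed OS. The missing time for early deaths and withdrawals holds only if PRO_LAS is missing without a follow-up form. For OS the point is confined to censoring at DT_EOS, which matters when closure is later than last contact.

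The reporting gap is that no 12-month Kaplan-Meier estimate with an interval is named for endpoints called 1-year, and the tables at that horizon are frequency distributions that do not account for censoring.

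The size is modest and rests on assumptions: about 3.8 points for one dropped early death among 14 patients with 6 other events, at most about 3.8 points for one patient lost early at 7/14, and 1.4 to 9.1 points for a crude count with 10% to 30% loss. The primary endpoints and the expansion decision rule are not affected.

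**What to change.** - **PFS event:** the earliest of DT_PROG, DT_FPRO, DT_DEAT and DT_DEATH, whichever form records it. In the expansion cohort, use the centrally reviewed progression date where one is available. This must stay conditional: Protocol 8.2.2.1 schedules central review to confirm 6-month status, and the PFS row lists no central date.
- **PFS censoring:** the last evaluable tumour assessment (DT_MEAC), or DT_STA if there is none. This also gives early withdrawals a defined time.
- **OS:** keep the event logic. Censor living patients at the latest known-alive date (DT_LNEW).
- **Reporting:** give 12-month Kaplan-Meier PFS and OS with 95% CI, in place of or beside Tables 14.3 and 14.4. Keep medians where they are reached.

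The cost is SAP wording and minor reprogramming of two derived variables and two tables. Apart from the central progression date, the fields named here already appear in SAP 3.2.2.1. The downside is slightly shorter follow-up credit, because patients are censored at their last evidence rather than at study closure.
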